### Time of Follow-Up for PFS

A plot will be generated to compare planned and actual relative day of tumor assessments by treatment group. A Kaplan-Meier plot for PFS follow-up duration will also be generated to assess the follow-up time in the treatment groups reversing the PFS censoring and event indicators.

### 6.2.3. Pharmacokinetic Endpoints

The following pharmacokinetic analyses will be conducted by treatment group.

Standard parameters including, but not limited to  $C_{max}$ ,  $C_{trough}$ ,  $T_{max}$ ,  $AUC_{\tau}$ ,  $t_{1/2}$ , CL, and  $V_{ss}$ , as data permit will be estimated using non-compartmental analysis.

Descriptive statistics (n, mean, SD, %CV, median, minimum, maximum, geometric mean, its associated 95% confidence interval and geometric %CV) of serum concentrations for PF-05082566 and MK-3475 will be presented in tabular form by study day, cycle, dose and nominal time. Concentrations with zero values will be excluded from the calculation of geometric means, its associated 95% confidence interval and geometric %CV. Linear and semi-log plots of median serum concentrations vs nominal time will be prepared by study day, cycle and dose. Similar plots will be prepared for each individual patient's serum concentrations.

Pharmacokinetic parameters will be listed and summarized by cycle and dose using descriptive statistics (n, mean, SD, %CV, median, minimum, maximum, and geometric mean, its associated 95% confidence interval and geometric %CV). Dose-normalized parameters (eg,  $C_{trough}$ ,  $C_{max}$  and AUC) will also be listed and summarized. Pharmacokinetic parameters with zero values will be excluded from the calculation of geometric means, its associated 95% confidence interval and geometric %CV.

$C_{max}$  and  $C_{trough}$  for PF-05082566 may be plotted against dose (using a logarithmic scale). These plots will include individual patient values and the geometric means for each dose. These plots will be used to help understand the dose proportionality for PF-05082566.

#### 6.2.4. Population Pharmacokinetic Endpoints

Pharmacokinetic CCI data from this study may be analyzed using modeling approaches and may also be pooled with data from other studies to investigate any association between PF-05082566 and MK-3475 exposure and biomarkers or significant safety/efficacy endpoints. The results of these analyses, if performed, may be reported separately.

#### 6.2.5. Biomarker Endpoints

For tumor biopsy samples, the mean and standard deviation, median, and minimum/maximum levels of biomarker measures, including but not limited to percentage of CD3-positive T cells, will be determined at baseline and post-treatment. For each pair of specimens, the percent change from baseline of these same parameters will also be calculated. The minimum percent change from baseline needed to declare proof of pharmacology will be based on assay precision and size of the expansion cohort.

CCI The statistical approach will examine correlations of biomarker results with pharmacokinetic parameters and measures of anti-tumor efficacy.

CCI

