32. **Follow Up:** Patients should be evaluated up to 90 days after last dose of study treatment. Refer to the protocol for specific guidelines. Patients continuing to experience toxicity following discontinuation of study treatment will continue to be followed at least every 4 weeks until resolution or determination, in the clinical judgment of the Investigator, that no further improvement is expected. PK and immunogenicity samples should be collected as described in the PK and Immunogenicity Assessment section in Schedule of Activities ([Table 3](#)). Patients whose disease has not progressed at the end of treatment will enter into disease follow-up. During this follow-up period, patients will have disease assessments performed every 12 weeks \pm 7-days. Once patients have exhibited disease progression or began a new anti-cancer therapy, or 6-month follow-up from the date of the first dose of the last enrolled patient, whichever occurs first, they will be withdrawn from the study. See [Section 4.3.1](#) Contraception for guidelines on contraception checks during this period.
33. **De novo tumor biopsy for biomarker assessment (Dose escalation):** For patients in dose-escalation cohorts, unscheduled optional de novo tumor biopsies may be collected at the discretion of the investigator and sponsor to support the assessment of disease progression.
34. **De novo tumor biopsy for biomarker assessment (Expansion cohorts):** Mandatory for patients in expansion cohorts only. A de novo biopsy will be required at study entry followed by a second biopsy at the time of the Week 9 scans (after 3 cycles of treatment).
35. **Continued Treatment Beyond Cycle 8:** This will be on a reduced visit schedule (Day 1 of each cycle), or as clinically indicated.
36. **Thyroid Function Tests:** To be collected every 2 cycles for the first 8 cycles, and then every 4 cycles (Cycles 1, 3, 5, 7, 11, 15 etc.).
37. **Hepatitis B and C Tests:** Conduct tests for hepatitis B surface antigen, core antibody, and anti-hepatitis C. Other tests may be conducted per standard practice to confirm an active hepatitis infection.

Table 4. Required Laboratory Tests

SAFETY LABORATORY REQUIREMENTS	
Refer to the Schedule of Activities table for specific timepoints and instructions	
Assessments	
Hematology Panel:	Chemistry Panel:
Absolute Neutrophil Count	Sodium
Hemoglobin	Potassium
	Total Calcium
Platelet Count	Creatinine
WBC with differential (5-part if available)	Albumin

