7.6. Tumor Biopsies for Mechanistic Exploratory Biomarkers

Tumor growth inhibition following treatment with 4-1BB agonist monoclonal antibodies or with PD-1 antagonist monoclonal antibodies has been associated with increases in tumor-infiltrating lymphocytes. Paired de novo tumor biopsies are mandatory for the patients enrolled in the expansion cohorts in order to determine whether the combination of PF-05082566 and MK-3475 has this effect. A de novo biopsy will be required at study entry followed by a second biopsy at the time of the Cycle 3 tumor assessment. For patients in dose escalation cohorts, unscheduled optional de novo tumor biopsies may be collected at the discretion of the Sponsor and Investigator to support the assessment of disease progression. Biomarkers that will be assayed may include but will not be limited to IHC assessment of tumor-infiltrating lymphocytes, PD-L1 IHC, quantitation of T cell receptor sequences, and gene expression.

Please refer to the Study Manual for details pertaining to specific days of sample collection, and sample preparation and shipping

CCI

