9.5.1.4. Statistical Analysis of Biomarker Endpoints

For tumor biopsy samples, the mean and standard deviation, median, and minimum/maximum levels of biomarker measures, including but not limited to percentage of CD3-positive T cells, will be determined at baseline and post-treatment. For each pair of

specimens, the percent change from baseline of these same parameters will also be calculated. The minimum percent change from baseline needed to declare proof of pharmacology will be based on assay precision and size of the expansion cohort.

CCI [REDACTED] The statistical approach will examine correlations of biomarker results with pharmacokinetic parameters and measures of anti-tumor efficacy.

CCI [REDACTED]

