## **5. GENERAL METHODOLOGY AND CONVENTIONS**

### **5.1. Hypotheses and Decision Rules**

#### **5.1.1. Hypotheses and Sample Size Determination**

No formal statistical hypothesis testing is planned.

Due to the dynamic nature of the Bayesian allocation procedure, the sample size of the Time-to-Event Continual Reassessment Method (TITE-CRM) cannot be determined in advance. The maximum sample size is set as 45 for dose escalation cohorts in order to have a reliable and accurate estimate of the MTD based on simulation results. Based on probability theory, a sample size of 45 will ensure the estimates of any binary variable (eg, objective response rate) have a 95% confidence interval of width  $<0.30$ . A sample size of 45 also enables the detection of any unexpected toxicity that occurs at 5% rate (in a non-dose-dependent fashion) with a probability of 0.90, and that occurs at 10% rate with a probability of 0.99.

A stopping rule will also be implemented if:

- Maximum sample size ( $n=45$ ) is reached; or
- 9 evaluable patients have been treated at the estimated MTD; or
- All doses appear to be overly toxic and the MTD cannot be determined in the current trial.

Additional patients will be required for expansion cohorts. The total number of patients in expansion cohorts will be determined based on emerging data from this study, cancer indication, and the patient population of interest.

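### The proof-of-pharmacology threshold for the paired biopsies names assay precision as its only source of variability and leaves out biopsy-to-biopsy variation

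*SAP*

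**What the plan says.** SAP 6.2.5 sets the rule: "The minimum percent change from baseline needed to declare proof of pharmacology will be based on assay precision and size of the expansion cohort". Protocol 9.5.1.4 agrees that the threshold "will be based on assay precision and size of the expansion cohort".

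The quantity compared with the threshold is a change between specimens: "For each pair of specimens, the percent change from baseline of these same parameters will also be calculated". The one measure named is CD3-positive T cells ("including but not limited to percentage of CD3-positive T cells").

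The specimens come from two procedures. Footnote 34 of the protocol's Schedule of Activities states: "A de novo biopsy will be required at study entry followed by a second biopsy at the time of the Week 9 scans". Protocol 7.6 gives the purpose: "Paired de novo tumor biopsies are mandatory for the patients enrolled in the expansion cohorts in order to determine whether the combination" raises the number of tumor-infiltrating lymphocytes.

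Cohort size, the second input to the threshold, is left open in SAP 5.1.1: "The total number of patients in expansion cohorts will be determined based on emerging data from this study". The same section says that no formal hypothesis test is planned. The readable text gives no numerical threshold, assay CV, between-biopsy variance or error rate. It does not say whether the rule applies to each patient or to a cohort summary.

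**The concern.** The question is whether the drugs changed the tumor. The right comparison is with how far two biopsies from one patient differ when the drugs do nothing. That difference has at least three parts: assay error, sampling of different tissue, and change in the tumor over about nine weeks. The readable text does not require the same lesion to be sampled twice. Inclusion criterion 3 also lists excision among the preferred methods, and a lesion removed whole cannot be sampled again.

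Assay precision usually describes repeat measurement of one specimen, so it covers only the first part. Cohort size governs how the threshold scales with the number of pairs and adds no missing variance. A threshold built from these two inputs answers whether the assay could have produced the change, not whether untreated variation could have.

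At stake is a secondary mechanistic conclusion. The paired biopsies are a listed secondary endpoint (Protocol 2.2, SAP 3.2.5), and they are invasive and mandatory for every expansion patient. The primary DLT endpoint is not affected.

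**Working it through.** The plan gives no figure to reproduce for this rule, so what follows is an illustration on assumed inputs.

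**Assumptions.** Biomarker values are log-normal. The assay has log-scale SD sa and biopsy-to-biopsy variation has log-scale SD sb, each obtained from a CV by sqrt(ln(1 + CV²)). There is no drug effect. The threshold is set at one-sided 5% from assay variation alone. None of these values is in the documents.

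**Step 1: SD of a paired log change.**
- Same specimen assayed twice: sqrt(2) × sa.
- Two separate biopsies: sqrt(2) × sqrt(sa² + sb²).

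**Step 2: actual rate of false declaration.** For one pair, the threshold from assay error is 1.645 × sqrt(2) × sa. The chance of passing it is

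1 − Φ(1.645 × sa / sqrt(sa² + sb²)).

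For a mean log change over n pairs, threshold and true standard error both shrink by sqrt(n), so the rate is the same.

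**Step 3: results against the assumed 5%.**

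| Assay CV | Biopsy CV 10% | 20% | 30% | 50% | 75% | 100% |
|---|---|---|---|---|---|---|
| 10% | 12% | 23% | 30% | 37% | 40% | 42% |
| 15% | 9% | 16% | 23% | 31% | 36% | 39% |
| 20% | 7% | 12% | 18% | 26% | 32% | 35% |
| 30% | 6% | 9% | 12% | 19% | 25% | 29% |

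Worked cell: assay CV 30% gives sa = 0.294 and biopsy CV 10% gives sb = 0.100, so 1.645 × 0.294 / 0.310 = 1.56 and the rate is 6%. The rate equals 5% only if sb is zero. It reaches 10% when 1.645 / 1.282 = 1.283 = sqrt(1 + (sb/sa)²), that is, at sb of about 0.80 × sa.

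**Step 4: what this does to the threshold (assay CV 15%).** One pair needs +41% on assay error alone. With a biopsy CV of 30% it needs +115%, and with 50% it needs +217%. For a geometric mean over n = 20 pairs, +8% becomes +19% and +29%.

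**Step 5: the plan's percent-change scale.** If the rule uses the arithmetic mean percent change, that mean is above zero even with no effect. Its expected value is (1 + CVassay²)(1 + CVbiopsy²) − 1. For CVs of 15% and 50% this is 1.0225 × 1.25 − 1 = 28%. Simulation (100,000 trials per setting, assay CV 15%) gave these false-declaration rates:

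| Biopsy CV | n = 10 | n = 30 |
|---|---|---|
| 20% | 25% | 34% |
| 30% | 41% | 58% |
| 50% | 63% | 85% |
| 75% | 77% | 95% |

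On this scale the rate rises with cohort size.

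**Step 6: using the observed paired SD.** In simulated cohorts of 10, 20 and 40 pairs with no drug effect (20,000 per setting; sa 0.10-0.20, sb 0.20-0.80), a one-sided 5% one-sample t-test on the log changes rejected in 4.6% to 5.3%.

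**The case against.** The strongest reply is that the rule is not yet fixed. Both documents say only what the threshold will rest on. That wording does not forbid a margin for biopsy variation, and assay precision is not defined. Cohort size might enter differently, for instance by setting how many patients must pass a per-patient cut-off. Text beside the sentence is redacted, and the protocol calls the markers exploratory.

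Much of this stands, and it limits what can be claimed. A reader might infer that noise will be declared a drug effect far more often than intended. The documents do not support that: they state no intended error rate and plan no formal test, and the 5% used here is an assumption. A reader might also infer at least a doubling of the error rate. That holds only where biopsy variation is at least about 0.8 times assay variation; the table goes down to 6%. Nor can one say that cohort size makes no difference. That is true of a mean log ratio, but not of the arithmetic mean percent change.

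The reply does not remove the point. The operative sentence is complete and readable in both documents, and it names one source of variability for a comparison that has several. SAP Amendment 2 still names only those two inputs. Planning no formal test does not help either, since a threshold followed by a declaration is a decision rule. Its error rate matters whether or not it is called a test.

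**Conclusion.** The point holds as a wrong stated basis. The threshold rests on assay precision and cohort size, but it is applied to two biopsies about nine weeks apart. Any biopsy-to-biopsy variation pushes the false-declaration rate above whatever level assay precision would have given. The rate is therefore uncontrolled and probably inflated.

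The size cannot be determined from the documents. The 6% to 42% range assumes log-normal values, a one-sided 5% threshold, the assumed CVs in the table, and assay precision in its usual sense of repeat measurement.

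This should be corrected, but its reach is limited. A reader might suppose that it bears on the MTD or the recommended Phase 2 dose. No readable rule links the biopsy declaration to either: the biomarker example in Protocol 3.2 is sCD137 saturation, not T cells in biopsies. The paired biopsies also serve other analyses, including correlations with pharmacokinetics and efficacy.

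**What to change.** Amend the sentence in SAP 6.2.5 and Protocol 9.5.1.4 before the paired results are reviewed. Keep a minimum change, but take the error term from the pairs themselves. Suggested wording:

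> Proof of pharmacology will be declared at cohort level if (a) the lower limit of the two-sided 90% confidence interval (one-sided 5%) for the mean within-patient log ratio, post-treatment to baseline, computed from the observed SD of those log ratios, exceeds zero, and (b) the point estimate exceeds the stated minimum change resolvable by the assay. If the log ratios are clearly skewed, a signed-rank estimate and interval will be used. Assay precision will be reported as the change resolvable in a single patient.

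Condition (b) preserves the plan's effect-size requirement; an interval above zero alone would let a large cohort declare a trivial change. The minimum should be written as a number, stating whether it refers to one pair or to a cohort mean. In the illustration these are +41% and, for n = 20, +8%. A rule is also needed for zero values, for which a log ratio is undefined.

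The cost is wording in two documents, with no new biopsies or assays. The criterion will generally be harder to meet, because it carries the real paired variability, and with few pairs the interval will be wide. It does not separate a drug effect from a systematic change over nine weeks, which pairs from treated patients alone cannot do.

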#### 6.2.6. Endpoints for Immunogenicity Data of PF-05082566 and MK-3475

ADA/ Nab data will be listed and summarized for PF-05082566 and MK-3475 by dose and for the entire study population. The percentage of patients with positive ADA and Nab will be summarized by dose and overall study population (eg. at baseline, post-dose, treatment-induced, treatment-boosted or anytime of the study). For patients with positive ADA, the magnitude (titer), time of onset, and duration of ADA response will also be described, if data permit. The impact of ADA/Nab on PK, safety/efficacy will also be assessed, if data permit.

### 6.3. Other Endpoints

CCI

### 6.4. Subset Analyses

The number of patients expected in each treatment group is small and therefore no subset analyses are planned in this study.

### 6.5. Baseline and Other Summaries and Analyses

#### 6.5.1. Baseline summaries

The following analyses will be based on the FAS overall and separately by treatment group.

##### 6.5.1.1. Demographic characteristics

Demographic characteristics and physical measurements will be summarized by treatment group using the following information from the ‘Screening/Baseline Visit’ eCRF pages.

- Demographic characteristics:
  - Gender: Male, Female.
  - Race: White, Black or African American, Asian, American Indian or Alaska Native, Native Hawaiian or other Pacific Islander, Other, Unknown.
  - Ethnic origin: Hispanic/Latino (Yes/No).
  - Age (years): summary statistics.
  - Age categories :
    - < 65 years,  $\geq$  65 years.
    - < 65, 65-<75, 75-<85,  $\geq$  85 years.
  - Eastern Cooperative Oncology Group (ECOG) Performance Status: 0, 1, 2, 3, and 4.
- Physical measurements:
  - Height (cm).
  - Weight (kg).
  - Body Mass Index (BMI) (kg/m^2).
  - Body Surface Area (BSA) (m^2).

Site codes will be used for the determination of the patient's geographic region.

The listing of demographics and baseline characteristics will include the following information: patient identifier, treatment group, age, sex, race, ethnicity, height (cm), weight (kg), BMI (kg/m^2), BSA (m^2) and ECOG performance status.

#### **6.5.1.2. Medical History**

Medical history will be coded using the most current available version of Medical Dictionary for Regulatory Activities (MedDRA) and will be summarized from the 'Medical History' eCRF page. Medical history will be summarized as the numbers and percentages of patients by MedDRA preferred term (PT) as event category and MedDRA primary system organ class (SOC) as summary category. Each patient will be counted only once within each PT or SOC.

Medical history will be displayed in terms of frequency tables: ordered by primary SOC and PT in alphabetical order.

#### **6.5.1.3. Disease Characteristics**

Information on disease characteristics collected on 'Primary Diagnosis' and RECIST eCRF pages will be summarized overall and by treatment group. Summary statistics will be presented for the following.

From the 'Primary Diagnosis' eCRF page:

- Site of primary tumor.
- Primary diagnosis (summarize all categories collected in the 'Primary Diagnosis' eCRF page).
- Time since initial diagnosis to start date (months), defined as (start date – date of initial diagnosis)/30.4375.
- Time since diagnosis of local/regional recurrence of disease (months), defined as ('start date' – date of diagnosis of local/regional recurrence of disease)/30.4375.

From the RECIST eCRF page:

- Measurable disease (lesions) at baseline (Yes, No).
- Involved tumor sites at baseline.

#### **6.5.1.4. Prior Anti-Cancer Therapies**

The prior anti-cancer therapies are collected under the 'Previous systemic therapy', 'Prior Radiation Therapy' and 'Prior Surgery' eCRF pages.

The number and percentage of patients in each of the following anti-cancer therapy categories will be tabulated:

- Patients with at least one type of prior anti-cancer treatment.
- Patients with at least one prior anti-cancer drug therapy.
- Patients with at least one prior anti-cancer radiotherapy.
- Patients with at least one prior anti-cancer surgery.

Prior anti-cancer drug therapy will be summarized as follows based on the number and percentage of patients with the following:

- At least one prior anti-cancer drug therapy.
- Any prior anti-cancer therapy regimens: missing / 1 / 2 / 3 /  $\geq 4$ .
- Type of prior anti-cancer therapy.
- Prior anti-cancer immune therapy (including PD-1, PD-L1, anti-CTLA4, others).
- Intent of Therapy: Neo-Adjuvant / Adjuvant / Advanced – Metastatic.
- Best response: Complete Response (CR) / Partial Response (PR) / Stable Disease (SD) / Progressive Disease (PD) / Unknown / Not applicable (Adjuvant only). Best response is derived from the last treatment regimen.

The prior anti-cancer drugs will also be summarized based on the number and percentage of patients by the drug class and preferred term. A patient will be counted only once within a given drug class and within a given drug name, even if he/she received the same medication at different times. The summary will be sorted on decreasing frequency of drug class and decreasing frequency of drug name in a given drug class. In case of equal frequency regarding drug class (respectively drug name), alphabetical order will be used.

The listings of prior anti-cancer treatments and procedures will also be provided as follows. These will include the patient identification number, and all the relevant collected data-fields on the corresponding eCRF pages.

- Listing of prior anti-cancer drug therapies.
- Listing of prior anti-cancer radiotherapy.
- Listing of prior anti-cancer surgeries.

### **6.5.2. Study Conduct and Patient Disposition**

The following analyses will be performed based on the FAS overall and separately by treatment group.

#### **6.5.2.1. Patient Disposition**

The percentages below will be calculated based on the number of patients in the FAS.

- Total number of patients screened overall.
- Number of patients who discontinued from the study prior to treatment with study drug overall and by the main reason for discontinuation.
- Number and percentage of treated patients in each of the analysis sets defined in [Section 4](#).
- Number and percentage of patients with study drug ongoing (separately for each study drug when administered in combination).
- Number and percentage of patients who discontinued study drug overall and by the main reason for discontinuation of study drug (separately for each study drug when administered in combination).
- Number and percentage of patients who entered safety follow-up.
- Number and percentage of patients who discontinued safety follow-up overall and by the main reason for discontinuation.

In addition the following will be summarized:

- Number and percentage of treated patients by center.

